demonstrated that following an ablation for SVT, they may be particularly resistant to atrial fibrillation(44). From 20 participants, 1 experienced an episode of atrial fibrillation during the infusion protocol. The main limitation of this study is the fact that no control investigation was used, allowing a major confounder come into play; what would have happened if the participants had simply been observed for 18 minutes prior to their ablation? There is no information given on the frequency of clinical episodes of atrial fibrillation in the patients studied. We know that they had a long history of paroxysmal atrial fibrillation (7±6 years) without progression to persistent arrhythmia, but the frequency of paroxysms is not reported. We do not know what proportion of episodes of atrial fibrillation documented in the study as precipitated by isoprenaline would have occurred spontaneously. This concern is supported by results from a group who were deliberately looking for spontaneous episodes of atrial fibrillation. In their study of patients undergoing ablation under general anaesthesia, 27% (23 of 85 participants) had a spontaneous episode of atrial fibrillation (45). Interestingly, in only 7 of those 23 could atrial fibrillation be induced using iatrogenic means. The mechanism for an excess of episodes of spontaneous atrial fibrillation around the time of an ablation is easily hypothesised. Participants in the study were sedated but conscious and about to undergo a procedure that for many would have held significant trepidation. The autonomic interplay occurring at such times is exactly the type that has been demonstrated to be associated with initiation of paroxysms of fibrillation.

The same cofounding influence of the patient's own autonomic nervous system and the random occurrence of an episode of atrial fibrillation can be applied to many of the studies using isoprenaline induction. Early studies on atrial fibrillation initiation that used isoprenaline within their protocols investigated patient pools which were deliberately enriched with participants suffering from frequent episodes of arrhythmia (6±4 episodes per day(23)) often despite medication (had to have failed more than 2 drugs and still have an episode at least every 48 hours(19)).

Justification for Research

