 - Alternative hypothesis is that there is significant difference in the proportion of subjects who experience the occurrence of an episode of atrial fibrillation during the infusion protocol when comparing those who receive the isoprenaline infusion with those who receive the placebo infusion.

- Double blinded. Event rate in Isoprenaline group likely >30%. Event rate in placebo group likely <5%. For 90% power and 95% significance projected to need 31 participants per group.
- For higher event rates, fewer participants required. 15 participants per group for event rate >50%, 6 participants per group for event rate >80%.
- Aim to recruit 30 participants per group.

Experiment 3

- Does an infusion of the drug Isoprenaline induce Atrial Fibrillation in subjects following an ablation procedure for common type atrial flutter?
 - Null hypothesis under investigation is that there is no significant difference in the proportion of subjects who experience the occurrence of an episode of atrial fibrillation during the infusion protocol when comparing those who receive the isoprenaline infusion with those who receive the placebo infusion.
 - Alternative hypothesis is that there is significant difference in the proportion of subjects who experience the occurrence of an episode of atrial fibrillation during the infusion protocol when comparing those who receive the isoprenaline infusion with those who receive the placebo infusion.
 - Double blinded. Event rate in Isoprenaline group likely >30%. Event rate in placebo group likely <5%. For 90% power and 95% significance projected to need 31 participants per group.
 - Aim to recruit 35 participants per group.

Experiment 4

- Does an infusion of the drug Isoprenaline induce Atrial Fibrillation in subjects following an ablation procedure for either Atrio-Ventricular Re-entrant Tachycardia (AVRT) or Atrio-Ventricular Nodal Re-entrant Tachycardia (AVNRT)?
 - Null hypothesis under investigation is that there is no significant difference in the proportion of subjects who experience the occurrence of an episode of atrial fibrillation during the infusion protocol when comparing those who receive the isoprenaline infusion with those who receive the placebo infusion.

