 - Alternative hypothesis is that there is significant difference in the proportion of subjects who experience the occurrence of an episode of atrial fibrillation during the infusion protocol when comparing those who receive the isoprenaline infusion with those who receive the placebo infusion.
 - Double blinded. Event rate in Isoprenaline group likely <10%. Event rate in placebo group likely <5%. For 90% power and 95% significance projected to need 133 participants per group.
 - Descriptive data only, not feasible to power properly for this endpoint but may be reasonable to use a 1 sided test. Aim to recruit 35 participants per group.

Experiment 5

- Does a Cavo-tricuspid isthmus ablation for atrial flutter alter inducibility of atrial fibrillation using an isoprenaline infusion?
 - Null hypothesis under investigation is that the proportion of subjects in whom there is a change in the occurrence of atrial fibrillation between two administrations of an infusion of isoprenaline is not less than 20%. Where one administration is before and one is after an atrial flutter ablation procedure.
 - Alternative hypothesis is that the proportion of subjects in whom there is a change in the occurrence of atrial fibrillation between two administrations of an infusion of isoprenaline is less than 20%. Where one administration is before and one is after an atrial flutter ablation procedure.
 - Double blinded, placebo controlled. Event rate >30%
 - A 95%Cl of +/- 10% around an expected % disagreement of 10% would require 35 participants

Experiment 6

- Does an ablation procedure for a AVRT or AVNRT alter inducibility of atrial fibrillation using an isoprenaline infusion?
 - Null hypothesis under investigation is that the proportion of subjects in whom there is a change in the occurrence of atrial fibrillation between two administrations of an infusion of isoprenaline is not less than 20%. Where one administration is before and one is after an SVT ablation procedure.
 - Alternative hypothesis is that the proportion of subjects in whom there is a change in the occurrence of atrial fibrillation between two administrations of an infusion of isoprenaline is less than 20%. Where one administration is before and one is after an SVT ablation procedure.
 - Double blinded, placebo controlled. Event rate <10%
 - A 95%Cl of +/- 10% around an expected % disagreement of 10% would require 35 participants

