The Participant Information Sheet (PiS) will be specific to the part of the study a subject is being recruited to. The "Participant Information Sheet for those being recruited to the Cardiac Ward based Infusion Protocol" will be for those recruited to protocol Part A and includes subjects in group 1. The "Participant Information Sheet for those being recruited to the Cardiac Electrophysiology Laboratory Infusion Protocol" will be for those recruited to protocol Part B and includes those from groups 2, 3 and 4. The "Additional Information Sheet for those undergoing an ablation for Atrial Flutter or Atrial Fibrillation" will be given to participants recruited to groups 3 and 4.

Informed Consent

Informed consent to enter the study must be sought from each participant. This will be taken only after a full explanation has been given, an information leaflet offered and time allowed for consideration. Signed participant consent will be obtained. The right of the participant to refuse to participate without giving reasons will be respected.

Sample Size Calculation

The sample size calculation for estimation of the proportion of disagreement between repeated isoprenaline infusions in terms of ability to induce atrial fibrillation is based on the width of a 1-sided 95% confidence interval (CI). Assuming that the proportion of disagreement will be \leq 10%, a sample size of 35 patients would enable the proportion to be estimated with an upper limit of the 1-sided 95%CI for the proportion of \leq 20%.

A 1-sided CI is used as we only wish to ensure that the upper limit of the estimated proportion of disagreement is less than a given cut-off (20% has been chosen to indicate clinically significant disagreement); the lower limit of the CI is immaterial as the lower the proportion of disagreement the better, so we do not need to restrict this.

The sample size calculation for the randomised comparison of proportion of participants inducible in the placebo and isoprenaline arms is based on the chi-squared test. In the Pulmonary Vein Isolation Group, assuming that almost no participants in the placebo arm will be inducible (1%), and that the proportion of participants in the active drug (isoprenaline) arm who are inducible will be 30%, then 31 patients in each arm will be required for 90% power (assuming 2-sided significance of 5%).

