It is noted that previous literature suggests that the proportion of patients with a past history of atrial fibrillation who are inducible with isoprenaline is greater than 80%. This does not fit with our interpretation of day to day clinical practice and hence the study is powered to detect a far lower arte of inducibility. We will however perform a pre-specified interim analysis of the Pulmonary Vein Isolation Group once 10 participants with a past history of atrial fibrillation have been randomised to each arm of the study (Experiment 2). If a significant result is detected, enrolment to that block will be discontinued.

Statistical analysis

The analysis of the disagreement between repeated isoprenaline infusions in terms of ability to induce atrial fibrillation will estimate the proportion of disagreement with a 1-sided 95%CI for the proportion. A 2-sided 90%CI is first calculated and the upper limit of this interval gives the required upper limit of a 1-sided 95%CI. If the estimated upper limit is < 20% (the chosen cut-off for clinically significant disagreement) then agreement between repeated infusions will be considered acceptable.

The randomised comparison of proportion of patients inducible between placebo and isoprenaline will use the chi-squared test or the Fisher's exact test if numbers of patients in some categories are small.

It is anticipated that the rate of induced episodes of arrhythmia in a number of the groups where they are being given placebo infusion will approach zero. If the results of the study demonstrate that the rate of inducibility in the SVT group or atrial flutter group being given placebo infusion is zero, we would consider it acceptable to use one sided tests of significance.

Study Duration

We aim to recruit 235 participants over a 24 month recruitment period. It is anticipated that the majority of subjects will be recruited from the Bournemouth site.

- Start Date: 01/09/2014
- Estimated Date of End of Trial: 01/09/2017
- Maximum Duration of Participation: 12 months

Study Procedure

The study will require a minimum of 2 encounters with the study team. For subjects in the group of participants requiring the most visits, the study schedule requires 7 visits over 12 months. Usual care for this group would involve 4 visits to hospital, one of these is not required by the study participants and 3 are combined with study visits.

Infusion Protocol

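### The 31 and 133 per group rest on a 1% placebo rate, but Study Objectives prints <5% beside them, so the stated 90% power holds only near 1%

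*Protocol*

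**What the plan says.** Protocol, Study Objectives, Part B:

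- Experiments 2 and 3 expect more than 30% inducible on isoprenaline and add "Event rate in placebo group likely <5%. For 90% power and 95% significance projected to need 31 participants per group". Experiment 2 also quotes 15 per group for an isoprenaline rate above 50% and 6 per group above 80%, then sets its target: "Aim to recruit 30 participants per group". Experiment 3 aims for 35 per group.
- Experiment 4 expects fewer than 10% inducible on isoprenaline and states "Event rate in placebo group likely <5%. For 90% power and 95% significance projected to need 133 participants per group". It then calls the data descriptive, says proper powering is not feasible, and aims for 35 per group.

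Protocol, Sample Size Calculation: for the Pulmonary Vein Isolation Group the chi-squared calculation is made "assuming that almost no participants in the placebo arm will be inducible (1" per cent) against 30% on isoprenaline, "then 31 patients in each arm will be required for 90% power (assuming 2-sided significance of 5" per cent). No placebo rate is given there for the flutter or SVT groups.

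Protocol, Statistical analysis: the comparison uses the chi-squared test, or "the Fisher's exact test if numbers of patients in some categories are small". Placebo rates in several groups are expected to be close to zero.

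**The concern.** A sample size printed beside a range of rates is read as holding over that range. Here one section prints a placebo rate below 5% and another uses 1% to get the same number. With proportions this small the required size depends strongly on which is meant. A reader of Experiment 3 or 4 cannot find the 1%, because it is written only for the Pulmonary Vein Isolation Group.

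What is at stake is how a null result is read. If Experiment 2 or 3 shows no significant difference, it will be reported as coming from a comparison with 90% power. If the placebo rate were nearer 5% than 1% and the isoprenaline rate near 30%, the chance of missing the effect would be well above 10%. Experiment 2 also recruits one fewer per arm than the number it says it needs.

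**Working it through.** **Inputs.** Two-sided 5%, 90% power, chi-squared test, isoprenaline 30%, placebo 1% (Sample Size Calculation). Placebo <5%, isoprenaline 50% and 80% for the smaller sizes, and 10% for Experiment 4 (Study Objectives). Allocation 1:1 (Study Procedure, Part B). Planned sizes: 30 per arm (Experiment 2) and 35 per arm (Experiments 3 and 4).

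**Formula.** With placebo rate p0, isoprenaline rate p1 and p̄ = (p0 + p1)/2:

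n per group = [1.960·√(2p̄(1−p̄)) + 1.282·√(p0(1−p0) + p1(1−p1))]² / (p1 − p0)²

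**Step 1: reproduce the protocol's figures at 1%.** For 1% v 30%, p̄ = 0.155 and n = (1.003 + 0.601)²/0.29² = 30.6, so 31. In the same way 1% v 50% gives 14.4 (15), 1% v 80% gives 5.7 (6), and 1% v 10% gives 132.8 (133). All four printed figures come back exactly.

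**Step 2: the same formula across the printed range.** For 5% v 30%, p̄ = 0.175 and n = (1.053 + 0.650)²/0.25² = 46.4, so 47.

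| Placebo rate | n v 30% | n v 10% |
|---|---|---|
| 1% | 31 | 133 |
| 2% | 34 | 184 |
| 3% | 38 | 259 |
| 4% | 42 | 378 |
| 5% | 47 | 582 |

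At 5% the sizes for isoprenaline rates of 50% and 80% are 19 and 7. Other conventions at 5% (continuity correction, one-sided test, unpooled variance, arcsine) give 36 to 55 v 30% and 472 to 621 v 10%. None gives 31 or 133, so the choice of formula does not explain the mismatch.

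**Step 3: power of the planned sizes against 30% on isoprenaline, by the sizing formula.** Power = Φ{[(p1−p0)√n − 1.960√(2p̄(1−p̄))] / √(p0(1−p0)+p1(1−p1))}. For n = 30 at 5%: (1.369 − 1.053)/0.507 = 0.62, so 73%.

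| Per arm | Placebo 1% | 2% | 5% |
|---|---|---|---|
| 30 (Experiment 2 target) | 89% | 86% | 73% |
| 31 (stated need) | 90% | 87% | 75% |
| 35 (Experiment 3 target) | 94% | 91% | 80% |

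**Step 4: exact power at 5% v 30%, enumerating both binomials.**

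| Per arm | Chi-squared | Fisher |
|---|---|---|
| 30 | 78% | 63% |
| 35 | 84% | 74% |

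If Fisher is used only when an expected count is below 5, 30 per arm gives about 69%.

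**Step 5: is the 30 a slip?** Part A's 35 plus 2×30, 2×35 and 2×35 is 235, the recruitment total in Study Duration. So 30 is the working target for Experiment 2, although its stated need is 31.

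**The case against.** The strongest reply is that nothing is contradicted outright. A rate below 5% includes 1%, the Sample Size Calculation states 1% openly for the Pulmonary Vein Isolation Group, and Statistical analysis expects placebo rates near zero in several groups. On that basis 31 does give 90%. The isoprenaline rate is also a floor: at a 5% placebo rate, 31 per group reaches 90% once the isoprenaline rate is about 38% or more. This stands, and it makes the shortfall conditional. It does not repair the text, because 90% is printed beside a range over which it does not hold, with 30% as the protocol's own design value.

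Four stronger readings are tempting but not supported:

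- *Experiment 3 lacks 90% power.* Its 35 per arm exceeds the stated 31 and keeps 91% at a 2% placebo rate. The loss appears only further up the range.
- *Experiment 4's power claim fails.* The protocol says it cannot be powered and treats it as descriptive. No power is promised for its 35 per group.
- *The analysis rule forces Fisher's test and its lower power.* The rule names no threshold. On the usual expected count of 5, 30 per arm at 5% v 30% gives 30 × 0.175 = 5.25, and 35 per arm gives 35 × 0.155 = 5.4 even at 1%. Only 30 per arm at 1% falls below (30 × 0.155 = 4.65).
- *The Background's spontaneous rate should replace 1%.* It reports that "27% (23 of 85 participants) had a spontaneous episode of atrial fibrillation", but in a study under general anaesthesia with no observation window given. Here sedated patients are watched through a 10-minute infusion and a 10-minute washout, and the Pulmonary Vein Isolation Group must enter the laboratory in sinus rhythm. The figure makes 1% look optimistic for that group, but it is not a planning value.

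**Conclusion.** The point holds as a mismatch between stated rates and stated sizes. The 31, 15, 6 and 133 all come from a 1% placebo rate, while Study Objectives prints <5% beside 31 and 133 and gives 15 and 6 under the same Experiment 2 assumptions. With 30% on isoprenaline, the 90% power for 31 per group is lost as soon as the placebo rate moves appreciably above 1%.

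At the 5% bound, the chance of missing a true 30% v 5% difference with the planned 30 per arm in Experiment 2 is 27% by the sizing formula (22% exact chi-squared, 37% Fisher). With the planned 35 in Experiment 3 it is 20% (16% and 26%). At 1%, Experiment 2 falls short by one point (89%) and Experiment 3 exceeds 90%. In Experiment 4 only the quoted 133 is at odds with its stated rates.

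A reader might infer that the trial is underpowered. The documents do not show that: it depends on a placebo rate towards 5% together with an isoprenaline rate near 30%, and neither is established.

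**What to change.** In Study Objectives, give one placebo rate for each of Experiments 2, 3 and 4, consistent with the Sample Size Calculation. Either write 1% beside 31, 15, 6 and 133, or keep 5% and print 47, 19, 7 and 582. Extend the Sample Size Calculation to say which rate applies to the flutter and SVT groups.

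Reconcile 30 with 31 in Experiment 2, for example by keeping 30 and stating that it gives 89% at a 1% placebo rate by the sizing formula.

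Restate the power of the planned 30 (Experiment 2) and 35 (Experiment 3) per arm at placebo rates of 1% and 5%, naming the test. By the sizing formula these are 89% and 73% for 30, and 94% and 80% for 35. For Experiment 4, correct the figure or its rates and leave its descriptive status as it is.

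The cost is protocol wording. Recruitment and analysis are unchanged. The downside is that the stated power becomes less favourable.

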All parts of this investigation utilise a standard infusion protocol of a study drug. This study drug will be isoprenaline or placebo delivered in a double blinded fashion or will be open label isoprenaline dependent on which experiment it is being administered for. In all cases the infusion protocol will be identical as will the associated outcomes recorded. Although different experiments within the protocol call for different, statistically driven endpoints, the endpoints for every administration of a study drug infusion protocol are the same.

Outcome after which infusion would be stopped

- Occurrence of atrial fibrillation lasting greater than 30 seconds during study drug infusion protocol
- Occurrence of an arrhythmia other than atrial fibrillation, sinus tachycardia or junctional rhythm lasting greater than 30 seconds during study drug infusion protocol
- Discontinuation of the study drug infusion
 - o Severe tremulousness or anxiety
 - Complaints of severe chest tightness
 - Decrease in systolic blood pressure to consistently < 70mmHg
 - Electrocardiographic changes suggestive of myocardial ischaemia

Pre-specified outcomes to be recorded but which would not trigger cessation of infusion

- Occurrence of atrial fibrillation lasting less than 30 seconds during study drug infusion protocol
- Occurrence of an arrhythmia other than atrial fibrillation, sinus tachycardia or junctional rhythm lasting less than 30 seconds during study drug infusion protocol
- Time from start of infusion protocol to occurrence of atrial fibrillation
- Rate of infusion at time of occurrence of atrial fibrillation
- Maximum tolerated rate of study drug infusion prior to its cessation for any reason

Safety Endpoints associated with each infusion administration

- Death within 24 hours of start of study drug infusion protocol
- Stroke within 24 hours of start of study drug infusion protocol
- Myocardial Infarction within 24 hours of start of study drug infusion protocol

Observational Data

Collected from Additional Monitoring Group

Participants from some groups recruited will be offered the chance to have some additional follow up monitoring after their ablation procedure. This data will be purely descriptive and unpowered. It will be analysed looking at the following endpoints.

Observational Endpoints

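### Experiments 5 and 6 ask whether ablation alters AF inducibility but are judged by Experiment 1's repeatability rule, which ignores direction and, at Experiment 6's planned event rate, says nothing about ablation

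*Protocol*

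**What the plan says.** The Protocol (Study Objectives, Experiment 6) asks: "Does an ablation procedure for a AVRT or AVNRT alter inducibility of atrial fibrillation using an isoprenaline infusion". Under the null, the proportion of subjects whose AF outcome differs between the two infusions "is not less than 20%. Where one administration is before and one is after an SVT ablation procedure". Under the alternative, that proportion "is less than 20%. Where one administration is before and one is after an SVT ablation procedure". The planning line reads "Double blinded, placebo controlled. Event rate <10" per cent, a single rate that is not split into before and after ablation. Experiment 4, on post-ablation infusions in the same SVT group, gives "Event rate in Isoprenaline group likely <10" per cent.

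Experiment 5 uses the same pair of hypotheses for flutter ablation, again with a null proportion that "is not less than 20%. Where one administration is before and one is after an atrial flutter ablation procedure", and an event rate above 30%. Each of Experiments 1, 5 and 6 is sized at 35 participants for an expected disagreement of 10%, plus or minus 10 points.

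Under Endpoints, the three experiments share one primary endpoint, a change in outcome between the two infusions, with no direction. Under Statistical analysis, if the upper limit of the one-sided 95% interval is below 20%, "then agreement between repeated infusions will be considered acceptable". The Sample Size Calculation section justifies a one-sided limit on the ground that less disagreement is always better.

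**The concern.** The rule suits Experiment 1, where the same infusion is given twice with nothing in between and a low disagreement rate is what one hopes to show. Experiments 5 and 6 put an ablation between the infusions and ask whether it had an effect. The rule has two outcomes: agreement is acceptable, or acceptability has not been shown. Neither is a finding that ablation changed inducibility, and neither tells a rise from a fall.

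The problem is sharpest in Experiment 6. With few events at either infusion, few subjects can change whatever ablation does, so low disagreement reflects the low event rate. A reader told that agreement was acceptable would take it that SVT ablation leaves inducibility alone, when the same data could arise from ablation abolishing it.

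**Working it through.** **Inputs (Protocol).** Cut-off 20%; 35 pairs; expected disagreement 10%; event rate below 10% (Experiment 6) and above 30% (Experiment 5); upper one-sided 95% limit, taken as the upper end of a two-sided 90% interval. No interval method is named, so Wald and exact (Clopper-Pearson) limits are both shown.

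**The plan's own figure.** n = z² p(1−p)/d² with p = 0.10, d = 0.10 and z = 1.96 gives 3.8416 × 0.09 / 0.01 = 34.6, so 35. The stated 35 reproduces as a two-sided 95% Wald calculation.

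**Experiment 6: bound on the proportion changing.** A subject changes only if AF occurs at exactly one of the two infusions. Hence P(change) ≤ p_pre + p_post < 0.10 + 0.10 = 0.20 if the stated rate covers both infusions. Even two unrelated infusions at 10% each give 2 × 0.10 × 0.90 = 18%.

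**Experiment 6: complete abolition.** If p_post = 0, then P(change) = p_pre, below 10%, which is at or under the disagreement the plan expects.

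**When the rule is met with 35 pairs.** Upper limits by number of changes:

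| Changes | Wald | Exact |
|---|---|---|
| 2 | 12.2% | 16.9% |
| 3 | 16.4% | 20.7% |
| 4 | 20.3% | 24.3% |

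The rule is met with 3 or fewer changes (Wald) or 2 or fewer (exact).

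**Probability that abolition is called acceptable agreement.** P(X ≤ 3) and P(X ≤ 2), with X binomial(35, p_pre):

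| Pre-ablation rate | Wald | Exact |
|---|---|---|
| 10% | 0.53 | 0.31 |
| 8% | 0.69 | 0.46 |
| 5% | 0.90 | 0.75 |

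**Experiment 5.** Abolition from 30% gives 30% change, and the rule is met with probability 0.002 (Wald) or 0.0005 (exact), so here the null can be true and abolition is very unlikely to pass. Pooling directions still misorders the cases:
- unrelated infusions at 30% each, with no ablation effect: 2 × 0.30 × 0.70 = 42% change, outside the acceptable region;
- a one-way fall from 30% to 15%: 15% change, inside it. With 35 pairs this case passes with probability 0.21 (Wald) or 0.09 (exact).

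**What a directional test could do with 35 pairs.** With all changes one way, the exact two-sided McNemar p-value is 2 × 0.5^x: 0.0625 for 5 changes and 0.031 for 6, so at least 6 are needed. P(X ≥ 6) under abolition is 0.13 from 10%, 0.06 from 8% and 0.007 from 5%.

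**The case against.** **A false null is not a rejected null.** One might infer that Experiment 6 is bound to report no alteration. It is not: at a 10% pre-ablation rate, abolition misses the criterion in 47% (Wald) to 69% (exact) of trials. This stands, though a miss is only inconclusive and does not show an effect.

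**The rate below 10% may not cover both infusions.** Experiment 6 gives one unsplit rate, and Experiment 4's figure is post-ablation and only described as likely. The Background section cites evidence that patients may be particularly resistant to AF after SVT ablation, so the pre-ablation rate could be higher. If only the post-ablation rate is below 10%, a fall from 25% to 5% gives at least 20% change and the null is true. If only the pre-ablation rate is below 10%, the null needs a post-ablation rate above 10%. So the null is not impossible without qualification; the bound is conditional.

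**The 20% margin was pre-specified as clinically significant disagreement.** A 10% change is properly below it. That is fair for repeatability. It does not turn a repeatability margin into an answer about an ablation effect.

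**Experiment 5 is different.** Correct: its null can be true, and only the loss of direction carries over.

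**Two further inferences are not supported.** Experiment 1's expected 10% disagreement is no benchmark for Experiment 6: it concerns paroxysmal AF patients, event rate above 50%, open label on a ward, while Experiment 6 concerns sedated SVT patients without documented AF. A reader might also argue that stopping the infusion on an "Occurrence of an arrhythmia other than atrial fibrillation, sinus tachycardia or junctional rhythm lasting greater than 30 seconds during study drug infusion protocol" cuts short the chance to see AF before ablation more than after. That may be so, but the Protocol gives no rate for it and continues monitoring for 10 minutes after such a stop. It is a separate, unquantified matter.

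**A statistical analysis plan might add a directional table.** It might, but the Protocol itself fixes the hypotheses, the endpoint and the acceptance rule, so this is a stated rule that does not fit its question.

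**Conclusion.** The concern holds in this form. Experiments 5 and 6 apply a direction-blind repeatability rule to a question about an effect, and no outcome of that rule can show that ablation altered inducibility. In Experiment 6, provided the rate below 10% applies to both infusions, the null is false by the plan's own assumption, so rejecting it is uninformative. Complete abolition would be labelled acceptable agreement with probability between 0.31 and 0.90 for pre-ablation rates of 10% down to 5%, depending on the rate and the interval method. These figures assume 35 evaluable pairs. In Experiment 5 the defect is limited to the pooling of gains and losses. The documents do not support saying that Experiment 6 will certainly give a wrong answer, or that Experiment 5's null is untenable.

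**What to change.** Keep the 20% rule for Experiment 1 only. For Experiments 5 and 6, make the primary analysis the paired post-minus-pre difference in the proportion with AF in the isoprenaline arm, with a 95% confidence interval and exact McNemar as the test. Tabulate gained and lost pairs separately. Reword both sets of hypotheses to match.

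Label Experiment 6 descriptive, as Experiment 4 already is, and rest it on the estimate and interval. State that exact McNemar needs at least 6 one-way changes and has about 13% power for abolition from 10%, and less from lower rates, so a non-significant result must not be read as no effect.

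A sensitivity analysis for infusions stopped by a non-AF arrhythmia is optional and separate; it would reduce an already small number of pairs.

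The cost is wording in the Protocol and any analysis plan. No new data or participants are needed. Experiment 6 loses a formal conclusion, but one that it could not have supported.
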